4 STUDY POPULATION

4.1 NUMBER OF PARTICIPANTS

Two data collectors per province will be recruited to make the observations making a total of 10 data collectors for all the locations. Additionally, one caregiver per observation will be recruited by the data collectors to accompany them. Meaning 160 caregivers will be recruited. This is to avoid inconvenience to the caregiver and their affected under five children. In case, a community is encountered whereby the cases of pneumonia are very few, then the same caregiver will be accompanied for observation of an LHW, BHU and RHC of that locality as these facilities are closely located. If despite this practice, number of observations are not achievable per site than an additional site will be provided to the data collector to visit.

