2.1.2 Secondary Objectives

To determine the differences in pneumonia case management observed across the provinces of Pakistan in both public and private sector.

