The FLCF level will include observations made at the primary health care facilities which are the Basic Health Units (BHUs) and Rural Health Centres (RHCs). A basic health unit is located within a union council which is the smallest administrative unit in the Pakistani administrative system. Each basic health unit covers a catchment area of 25,000 households. Pakistan has around 5,290 BHUs although not all are functional. Services provided at BHU are promotive, preventive, curative and referral .LHWs refer patients usually to BHUs. RHCs provide in-patient service as compared to BHUs. They usually have 10-20 beds and cover a catchment area of 100,000 people. The RHC provides promotive, preventive, curative, diagnostics and referral services apart from the in-patient services. It also provides clinical, logistical and managerial support to the BHUs, LHWs, and dispensaries that fall within its geographical limits. RHC also provides medico-legal, basic surgical, dental and ambulance services. There are around 552 RHCs in Pakistan.

The practitioner level observations will include those of practitioners at both the private and public sector. The public sector will include observations made in outpatient departments of selected tertiary care hospitals across the study sites. Observations made at the private practitioner level will include selected solitary private clinics or clinics within private hospitals. The community and FLCF level will represent practices within the rural community and the practitioner level will represent practices within the semi urban/urban communities.

3.3 Type of Observations:

These will be participant, structured, disguised observations which will be done using a validated observation tool based on standard WHO pneumonia case management guidelines, developed in close collaboration with experts from University of Edinburgh. This tool will be pretested and translated into Urdu.

3.4 Data Collectors:

A team of data collectors, who will be healthcare professionals, will be trained on appropriate administration of the observation tool upon recruitment. The training will also include an introduction to pneumonia, its signs and symptoms, diagnosis and management according to WHO guidelines. A 3 day interactive training workshop will be conducted whereby mock excesses will also be conducted. A total of three trainings will be conducted whereby data collectors from Islamabad (capital), Punjab

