and KPK will have one training as their participants can be managed to be brought in one location due to close proximity. Sindh and Baluchistan participants will have two separate trainings.

3.5 Recruitment of Disguised Patients' Caregiver and Conduction of Observations:

Each data collector will be provided a pre-defined list of addresses whereby the observations will be made. He/she will go to the location and will search the nearby community for cases of pneumonia in children under five. Once the cases have been identified, their caregivers will be sought. These caregivers are the primary individuals providing direct care to the child. Usually, these are the mothers, fathers, grandmothers or guardians of the child. They will explained the purpose of the study and will be requested to participate in the study by acting as disguised caregivers to accompany the data collector to the health facilities and upon agreement will sign a consent form. This means that they will disguise as an acquaintance of the data collector who will take them to the healthcare professional to be observed. They will take the ill child along, give the history of that child to the healthcare professional and answer any relevant questions which will be asked by him/her and get the child examined and treated. In the meantime, the data collector will make the relevant observations based on the observation tool which will be filled after the visit. The data collector will not reveal that he/she is a healthcare professional. Additionally, the data collector will also take an audio recorder along to record the entire conversation which will help in filling up the observation tool later and also validate the visit. Once the visit is completed, the data collector will take the caregiver back to their premises and fill up the observation tool in tablets within one hour of the visit.

3.6 Project work-plan:

PROJECT ACTIVITIES	YEAR 1(Months)												YEAR 2
	1	2	3	4	5	6	7	8	9	10	11	12	
Ethical Clearance	X	X											
Staff Recruitment		X											
Tool Development			X										
Inception Meetings for development of implementation strategies			X										
Pretesting and Finalization of the tool				X	X								
Data Collections (Trainings, identification of study site/centers, observations)				X	X	X	X	X	X				
Data Analysis & Reporting										X	X	X	X

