7.2 Case Report Forms

Electronic CRFs (eCRFs) will be used for improved data quality, avoidance of manual data entry errors and confidentiality etc. It will include the following key points:

- ✓ Protocol ID
- ✓ Site code
- ✓ Subject ID

- ✓ Respondent Initials
- ✓ Respondent demographics (age, gender, educational level)
- ✓ Age of the youngest child
- ✓ Phone number
- ✓ Alternate phone number
- ✓ Prescription picture
- ✓ GPS location
- ✓ Date of visit
- ✓ Place of visit (LHW/BHU/RHC/Private clinic/Public tertiary hospital)
- ✓ Name of the healthcare provider
- ✓ Data collector initials/ID
- ✓ Time spent in consultation
- ✓ Visit checklist (as indicated by section 6.1)
- ✓ Reason of withdrawal from the study

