8 STATISTICS AND DATA ANALYSIS

8.1 SAMPLE SIZE CALCULATION

Considering this is a qualitative study therefore an approximate estimate of the sample will be provided. Event sampling will be employed whereby a pre-defined checklist of behaviours will be developed to record all occurrences. The sample size is based on point of theoretical saturation although we plan to conduct at least 32 observations from each of the four provinces and the federal capital (LHWS; 6, BHU Medical officer; 4, RHC medical officer; 4, private practitioner; 9, and public practitioner; 9). Thus a minimum of 160 observations will be conducted. Data will be collected over a period of six months.

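### Each province appears to be scored only by its own two data collectors, and Section 8.2 makes no use of the collector ID, so provincial differences cannot be separated from collector differences

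*Combined protocol and SAP*

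**What the plan says.** - **Collectors.** Section 4.1: "Two data collectors per province will be recruited to make the observations", 10 in all. The locations are four provinces and the federal capital.
- **Training.** Section 3.4 plans three trainings in total. Islamabad, Punjab and KPK share one. For the others, "Sindh and Baluchistan participants will have two separate trainings". On content: "A 3 day interactive training workshop will be conducted whereby mock excesses will also be conducted" (evidently mock exercises). The section does not say that these are the same in each workshop, scored, or compared.
- **Scoring.** Under Section 3.5 the collector searches the community for a case, attends the visit, and completes the tool within an hour, helped by an audio recording. Section 7 adds the prescription. No second rater is planned.
- **Collector identity.** The eCRF list in Section 7.2 includes "Data collector initials/ID".
- **Objective.** Section 2.1.2: "To determine the differences in pneumonia case management observed across the provinces of Pakistan in both public and private sector".
- **Size.** Section 8.1: "we plan to conduct at least 32 observations from each of the four provinces and the federal capital", made up of 6 LHWs, 4 BHU and 4 RHC medical officers, 9 private and 9 public practitioners.
- **Analysis.** Section 8.2 plans frequencies and percentages cross-tabulated by province. It contains no collector term, agreement measure, test or interval.

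**The concern.** If each pair works only in its own province, collector is nested in province. A stricter or more lenient pair then raises or lowers its province's percentages just as a real difference in practice would. Training session adds to this: Sindh and Baluchistan each differ from the rest in session as well as in collectors.

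Collector effects are plausible here. The same person selects the case and scores the visit. Section 5.1 allows doctors or nurses with as little as 6 to 12 months of paediatric experience. The tool's criteria are also sensitive: a visit is correct only with 12 of 12 history items or 6 of 6 examination items, so one item scored differently changes the label. More visits by the same collectors would not reduce this component. At stake is whether a provincial gap in the report can be read as a gap in provider practice.

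**Working it through.** **1. The plan's own counts.** 6 + 4 + 4 + 9 + 9 = 32 visits per location, and 32 × 5 = 160, which agrees with Section 8.1: "Thus a minimum of 160 observations will be conducted". Collectors: 2 × 5 = 10, which agrees with Section 4.1. With an equal split (assumed), 32 / 2 = 16 visits per collector. The documents give no alpha, power, effect size or collector variance, so there is no power calculation to reproduce.

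**2. What the design can separate.** There are two collectors in each of five locations, so variation between collectors within a location has 10 − 5 = 5 degrees of freedom. If no collector works in two provinces, no contrast separates province from the pair that scored it.

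**3. Illustration of size.** Assumptions, none from the documents: true practice 50% everywhere; between-collector SD *s* of 5, 10 or 15 points; a two-sided 5% comparison of two provinces that ignores collectors.

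- Naive SE = √(2 × 0.25 / 32) = 0.125.
- Collector variance of the difference = 2 × *s*² / 2 = *s*².
- Total SE = √(0.125² + *s*²).
- False-positive rate = 2 × P(Z > 1.96 × naive SE / total SE).

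| *s* | Total SE | False-positive rate, 32 v 32 |
|---|---|---|
| 5 points | 0.135 | 6.9% |
| 10 points | 0.160 | 12.6% |
| 15 points | 0.195 | 21.0% |

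The formula counts a little variance twice. With design effect 1 + 15 × *s*² / 0.25, the rates are 6.8%, 12.1% and 20.1%.

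**4. By sector, since the objective names both.** The private sector has 9 visits per province and the public sector 6 + 4 + 4 + 9 = 23. The naive SEs are √(0.5 / 9) = 0.236 and √(0.5 / 23) = 0.147. The formula in step 3 gives:

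| *s* | Private, 9 v 9 | Public, 23 v 23 |
|---|---|---|
| 5 points | 5.5% | 6.3% |
| 10 points | 7.1% | 10.5% |
| 15 points | 9.8% | about 17% |

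For private practitioners, sampling noise dominates.

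**5. Uncertainty.** A naive 95% half-width for 32 v 32 is 1.96 × 0.125 = 24.5 points. If collector variation is estimated on 5 degrees of freedom, the multiplier is about 2.57, and the total SEs in step 3 give about 35, 41 and 50 points.

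**6. What the collector ID can show.** A comparison of the two collectors in one province (16 v 16) has about 20% power for 50% v 70%, 42% for 50% v 80% and 71% for 50% v 90%. It would expose only large differences.

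**The case against.** The strongest reply is that Section 8.2 is descriptive and Section 8.1 calls the study qualitative. With no test or interval planned, there is no 5% error rate to inflate. That stands: a reader might infer from step 3 that the planned analysis has a false-positive rate of up to 21%, and the documents do not support that. The rates only show how far collector differences could pass for provincial ones. The descriptive label does not remove the problem, because the planned output is still percentages compared by province.

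A second reply is that safeguards exist. The tool is structured and pretested, collectors are licensed, visits are audio-recorded, and the prescription is kept. This stands in part. Recorded speech and written treatment leave less room for rater differences, so one SD for all four endpoints is a simplification. Audio cannot confirm most examination items, such as pallor, rash or chest indrawing, and the same collector uses the recording.

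A third reply is that the collector ID is a weak instrument, and this also stands. Each collector has a separate list of addresses and finds the cases, so differences within a pair mix rater, site, cadre and case mix. A bias shared by both members of a pair, including one from their common training, stays hidden. A reader might infer that the ID and the mock exercises already amount to a check. They do not: no analysis uses the ID, and nothing says that the exercises are shared or scored.

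Finally, confinement of each pair to its own province is implied by recruitment per province and by training arrangements. It is not stated outright.

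**Conclusion.** The point holds as a limit on interpretation. As written, the plan cannot distinguish provincial practice from collector behaviour, and this bears directly on the secondary objective. It does not show that collectors do differ, or that any provincial difference will be false.

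The size is unknown. Under the assumptions stated (50% practice, SD of 5 to 15 points, equal split of visits), the illustrative false-positive rate is about 7% to 21% for pooled provinces and about 5.5% to 10% for private practitioners alone. It rests on each pair staying in its own province. The matter should be addressed because the remedy is cheap, but it does not undermine the primary, descriptive objectives in the same way.

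**What to change.** 1. **Section 3.4.** Use one identical set of scripted mock cases in all three workshops. Have all 10 collectors score them independently, report item agreement by collector and by session, and retrain on discordant items before fieldwork. This is the step that can expose a scoring bias shared by a pair or a session.
2. **Section 8.2.** Tabulate each endpoint by collector within province beside the provincial percentages, using the ID already captured. If intervals or tests are reported, base them on between-collector, within-province variation (5 degrees of freedom, t about 2.57).
3. **Limitation.** State that the collector ID cannot show a bias shared by both collectors in a province, and that differences between collectors also reflect site, cadre and case mix.

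The cost is a little more training and analysis work, with no new staff or travel. Provincial differences will be shown with wider uncertainty.

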4.2 INCLUSION CRITERIA

4.2.1 INCLUSION CRITERIA OF DISGUISED CAREGIVERS:

- Caregivers of children under five years of age. These are those individuals who provide direct care to the child. These could either be a mother, father, grandmother or guardian.
- The child under five under that caregiver's household must have symptoms of pneumonia/severe pneumonia as indicated in section 6.1
- Caregivers consenting to be a part of the study.

4.2.2 INCLUSION CRITERIA OF HEALTHCARE PROFESSIONALS UNDER OBSERVATION

4.2.2.1 LHWs:

- Those who have been practicing as LHWs for more than one year as identified by talking to the community.
- Those who belong to the catchment area of the selected study sites

4.2.2.2 BHUs:

Functional BHUs with at least one licensed healthcare provider.

4.2.2.3 RHC:

Functional RHCs with at least one licensed healthcare provider.

4.2.2.4 Public Practitioners:

Paediatricians working in a government tertiary healthcare facility as a full time employee.

In case the facility/location does not have specialist paediatricians, then general physicians working full time within that facility.

4.2.2.5

4.2.2.6 Private Practitioners:

Full time/part time private paediatric practitioners working in either their private clinics or in private hospitals.

In case the facility/location does not have specialist paediatricians, then general physicians working within that facility.

4.2.3 EXCLUSION CRITERIA

4.2.3.1 EXCLUSION CRITERIA FOR DISGUISED CAREGIVERS:

Caregivers of children under five suffering from comorbidity with pneumonia.

4.2.3.2 EXCLUSION CRITERIA FOR HEALTHCARE PROFESSIONALS UNDER OBSERVATION

BHUs or RHCs run by non-licensed healthcare professionals as there are certain locations whereby due to lack of licensed healthcare professional's facility technicians tend to attend to the patients based on their experience.

5 PARTICIPANT SELECTION AND ENROLMENT

5.1 IDENTIFYING PARTICIPANTS

Data collectors will be licensed healthcare professionals (doctors or nurses) with at least one 6-12 months of experience working in the field of paediatrics. They will be recruited after interviews with the selection team (Investigators and project manager) upon giving advertisements for posts of data collectors.

For selection of the LHWs to observe them, a randomly selected rural community through our computerized system will be generated from where the caregivers will be selected to act as disguised ones. Additionally, a complete list of functional RHCs and BHUs will be obtained from the corresponding district health office (DHO) which is the administrative authority for these centres. From that list, four BHUs and four RHCs per province will be randomly selected using a lottery method. For sampling of the practitioners, a list of tertiary care facilities will be obtained from the health department of each province and a list of private clinic and private hospitals from their corresponding directories. These lists will be used to randomly select five practitioners each from public and private sector. Once the BHU, RHC, private and public practitioner sites have been selected, disguised caregiver will be recruited and observations made. In case a healthcare provider is not available or if a facility has been closed down, the caregiver will be provided an alternate address.

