Healthcare in Pakistan is provided through two sectors; Public and private. The public sector includes community health workers, referred to as Lady Health Workers (LHWs) working under the National Program for Family planning and Primary Health Care. It also includes the First Level Care Facilities referred to as Basic Health Units (BHUs) and Rural Health Centres(RHCs) and district/tertiary care hospitals. The private sector includes the private clinic and private hospitals. The public sector provides healthcare free of cost or with minimal charges whereas the private sector is expensive as patients spend out-of-pocket for health service in this sector. This accounts to the wide difference of quality of care across both the sectors as the public sector is not funded adequately by the government to provide high quality services, due to only 2% of the GDP assigned to healthcare. Irrespective of the public and private sector, case management of pneumonia in children under five is supposed to be followed uniformly across all sectors as training of the healthcare providers is standard across all cadres of care under various programs in the country. Despite that fact, the mortality and morbidity rate due to pneumonia in children under five remains unchanged in the country.

1.2 1.2. RATIONALE FOR STUDY

WHO and UNICEF have developed multiple action/ intervention plans to curb pneumonia related morbidity and mortality in children under five and based on those plans Pakistan has launched multiple national programs. These programs include the National ARI control program which was launched in 1989 with the main objectives of reducing severity and mortality due to pneumonia and rationalize the use of

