2 STUDY OBJECTIVES

2.1 OBJECTIVES

2.1.1 Primary Objective

To assess the standard practices of pneumonia case management at three levels of health care; community level, first level care facility and practitioner level, across Pakistan.

To assess the standard practices of pneumonia case management in the private sector across Pakistan.

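### Section 5.1 draws five public and five private practitioners, but the minimum of 160 observations in section 8.1 needs nine of each in every area

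*Combined protocol and SAP*

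**What the plan says.** Section 8.1 of the combined protocol and SAP sets a floor of 32 observations in each of five areas. The split is 6 lady health workers (LHWs), 4 basic health units (BHUs) and 4 rural health centres (RHCs), with the remainder given as "private practitioner; 9, and public practitioner; 9". It concludes: "Thus a minimum of 160 observations will be conducted". Section 4.1 repeats 160 as the number of caregivers, at one caregiver per observation.

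Section 5.1 describes the selection. For primary care facilities, "four BHUs and four RHCs per province will be randomly selected using a lottery method", which agrees with 8.1. For practitioners, lists of tertiary facilities and of private clinics and hospitals are obtained, and then: "These lists will be used to randomly select five practitioners each from public and private sector". That sentence gives no area. The sentence after it changes the unit: "Once the BHU, RHC, private and public practitioner sites have been selected".

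On sectors, section 1.1 places LHWs, BHUs, RHCs and district and tertiary hospitals in the public system, and adds: "The private sector includes the private clinic and private hospitals". Section 2.1.1 gives the private sector a primary objective of its own: "To assess the standard practices of pneumonia case management in the private sector across Pakistan". The secondary objective in 2.1.2 concerns differences between provinces in both sectors.

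**The concern.** The selection procedure and the sample-size floor give different numbers for the same two strata. The BHU and RHC counts match across the two sections; only the practitioner counts differ.

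Section 3.5 gives data collectors a list of addresses fixed in advance. If that list is built from 5.1, it holds five practitioner addresses per sector, not nine. Either the minimum is missed, or four of the nine in each sector are found in the field and were never part of the random draw.

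The shortfall is also uneven. Private practitioners are the only source of private-sector data, so the whole reduction in that stratum falls on one of the two primary objectives, whereas the public sector keeps its LHW, BHU and RHC observations.

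**Working it through.** **Inputs.** Per-area counts of 6, 4, 4, 9 and 9, and five areas, from 8.1. Four BHUs, four RHCs, and five practitioners per sector, from 5.1. Section 5.1 gives no number of LHWs, so 6 is carried over from 8.1. The capital is counted as an area, as in 8.1; 4.1 does the same when two data collectors per province make 10.

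**The plan's own figure.** 6 + 4 + 4 + 9 + 9 = 32 per area; 32 × 5 = 160. Section 8.1 is internally consistent and agrees with the 160 caregivers in 4.1.

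**The draw in 5.1, per area, one observation each.** 6 + 4 + 4 + 5 + 5 = 24 per area; 24 × 5 = 120. The shortfall is 160 − 120 = 40, and 40/160 = 25%.

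**Other readings of 5.1.**
- Five per sector for the whole country: (6 + 4 + 4) × 5 + 10 = 80.
- Five sites per sector per area supplying nine observations: 9/5 = 1.8 per site on average. This recovers 160, but no section gives a number per site or an allocation.

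**Where the loss falls (per-area reading; sectors as in 1.1).**

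| Stratum | Under 8.1 | Under 5.1 | Change |
|---|---|---|---|
| All practitioners | 18 × 5 = 90 | 10 × 5 = 50 | −44% |
| Private | 9 × 5 = 45 | 5 × 5 = 25 | −44% |
| Public (LHW + BHU + RHC + tertiary) | 23 × 5 = 115 | 19 × 5 = 95 | −17% |
| Total | 160 | 120 | −25% |

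**Effect on a percentage within one area.** One observation moves a private percentage by 100/9 = 11.1 points at nine and 100/5 = 20.0 points at five. For the public sector the figures are 100/23 = 4.3 and 100/19 = 5.3 points.

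**Effect on the national private-sector estimate.** The 95% Wilson half-width is z/(1 + z²/n) × √(p(1−p)/n + z²/(4n²)), with z = 1.96. The documents give no expected proportion correct, so two values are assumed, and observations are treated as independent.
- p = 0.5: n = 45 gives 14.0 points; n = 25 gives 18.2 points.
- p = 0.2: n = 45 gives 11.5 points; n = 25 gives 15.1 points.

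**The case against.** The best defence is that 8.1 counts observations whereas 5.1 describes a draw from lists of facilities, and its next sentence speaks of sites. A tertiary outpatient department or a private hospital may hold several practitioners, and describing the observations as made once (6.1) does not bar observing two practitioners at one site. Four sites with two observations and one site with one would give nine. On that reading nothing is lost and only an allocation rule is missing. This stands as a possibility, and it is why 120 must be stated as conditional. But 5.1 says practitioners, no section supplies the allocation, and 3.2 allows stand-alone private clinics, where a second practitioner may not exist.

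A second point is that 160 appears consistently in 8.1 and 4.1, so five may simply be a slip. That is plausible, but 5.1 is the text from which the sample would be drawn, so the slip still needs correcting.

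Third, 8.1 calls the sample approximate and based on saturation, and 8.2 plans only frequencies and percentages, with no intervals or tests. The Wilson figures are therefore this review's own illustration and not a criterion of the plan. So is the pooled public cell, which rests on the background text in 1.1. The conflict does not depend on either: 8.1 still sets a floor per area and a minimum total.

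Finally, 5.1 offers alternate addresses and 4.1 an additional site. The first replaces a provider who is unavailable or a facility that has closed. The second applies where there are too few pneumonia cases. Neither is a planned route from five to nine.

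**Conclusion.** The concern holds: 5.1 and 8.1 conflict, and the draw as written does not provide for the stated minimum. Taken per area with one observation per practitioner, the total is 120 instead of 160 (−25%), and private-sector observations fall from 45 to 25 (−44%). The per-area reading is supported by the preceding sentence of 5.1, which counts per province, and by the provincial source of the tertiary lists; 5.1 does not state it. Across readings the total runs from 80 (five nationwide) through 120 to 160, the last only with an allocation of observations to sites that the plan does not contain. The documents do not settle whether five or nine is intended, though the caregiver count in 4.1 agrees with nine. This should be corrected before practitioners are selected.

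**What to change.** Make 5.1 and 8.1 agree, in one of two ways.

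- **If nine is intended:** state in 5.1 that nine public and nine private practitioners are drawn at random in each province and in the federal capital. The 160 in 8.1 and 4.1 then stands.
- **If five is intended:** restate 8.1 as 24 observations per area and a minimum of 120, and 4.1 as 120 caregivers.

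In either case, say in 5.1 whether the unit drawn is a practitioner or a site. If a selected site is meant to supply more than one observation, give the number per site that makes nine, and say how practitioners within the site are chosen.

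The cost is wording: 5.1 alone for nine, or 5.1, 8.1 and 4.1 for five. No data field is added, and choosing nine adds no observations beyond the 160 already planned.
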